6.2. Screening/Qualification Visit (At Least Day -30 to Day 1, Visit 1)

Any protocol-specified study qualification procedures or tests not already done as part of routine care will be conducted only after the subject signs the ICF and before randomization.

Central laboratory specimens will be collected to determine the baseline qualification of the subject for inclusion/exclusion criteria and evaluation of particular analytes over time across the global study except for INR and aPTT which are performed at the clinical site or local laboratory.

All subjects at the Screening Visit should be assessed for INR and aPTT evaluated at the local laboratory.

Prior to signing the ICF, potential subjects and their parent(s) or guardian(s) will have the study risks and benefits explained, the associated ICF and assent form, if applicable, will be reviewed, and all questions answered for them. Written informed consent must be signed by the parent(s) or guardian(s) of all subjects, and assent obtained from the child, when and where applicable, prior to entry into the study.

- The Screening eCRFs must be completed for every subject with a signed ICF. Any protocol-specified study qualification procedures/tests identified for the Screening Visit, not already done as part of routine care within 2 weeks of the Screening Visit will need to be conducted after the parent(s) or guardian(s) signs the ICF as part of the Screening/Qualification Visit.
- The following study qualification procedures for the Screening/Qualification Visit must be completed to ensure that the subject is eligible for the study.

Review inclusion/exclusion criteria

Record demographic information (date of birth/age, sex, ethnicity, and race)

Record medical/surgical history, including:

- TE history and bleeding history since diagnosis of underlying disease and within the past 3 months
- Date of diagnosis of underlying disease

Record prior medication (up to 30 days prior to Screening). Anticoagulant and antiplatelet therapy will be captured up to 3 month prior to Screening Visit

Assess for and record AEs and concomitant medications.

Perform physical examination (Section 9.9) including:
- Vital signs (BP, heart rate, and body temperature after resting in a sitting or supine position [Note: the appropriate cuff size base on arm circumference will be used.])
- Height and body weight (may be performed by an Investigator or other healthcare provider designated by the Investigator).
- An aPTT and INR assessment will be done for all subjects at Screening at local laboratory. Ensure that the subject qualifies with regard to the following central safety laboratory and radiology tests for exclusion criteria:

Echocardiogram. Note: Valid echocardiograms are images taken within 5 weeks prior to Randomization Visit. Note: The presence of a thrombus will disqualify the subject from the study.

Liver function assessments (ALT, AST, TBL, ALP) (central laboratory)

aPTT and INR (assessed locally)

Serum chemistry panel, serum creatinine, and eGFR (central laboratory)

Hematology (central laboratory)

Urinalysis (at central laboratory if dipstick is abnormal)

Note: Urinalysis can be done at local laboratory. Results of urinalysis performed at Screening by local laboratory may be used for qualification

• To expedite qualification and randomization for subjects living a distance from the Investigator site, the site may choose to use their local laboratory for screening eligibility labs. The sample should be split with analysis at both the central laboratory as well as the local laboratory. For the purpose of eligibility, the local laboratory results (aPTT, INR, ALT, TBL, eGFR, and platelet) will be utilized and entered into the eCRF.

If subjects are fulfilling eligibility conditions at the Screening/Qualification Visit, the Investigator has the option to randomize the subject at any time within 30 days. The Screening Visit and Randomization Visit may occur on the same day.

6.3. Randomization (Day 1, Visit 2)

Investigators will maintain a confidential subject identification code list of names of all subjects randomized to study to allow the Investigator to reveal the identity of any subject when necessary. If all procedures and tests done before randomization confirm the subject's eligibility (Section 6.2) for the study, then the IXRS will be contacted to randomize the subject.

Urine pregnancy test in females of childbearing potential by definition are those females that have reached menarche and until becoming postmenopausal unless permanently sterile (defined as no menses for 12 months without an alternative medical cause).

Randomization may occur in IXRS the day prior to dosing for clinical logistics. Screening Visit and Randomization Visit may occur on the same day. The first dose of study treatment may occur on Day 1 or Day 2 (see Section 5.2.4)

The following activities should be done at the time of randomization.

NOTE: For therapeutic monitoring of SOC the Investigator will use discretion to decide when and how often to repeat INR or anti-FXa levels or aPTT measurements after randomization. These measurements will be taken and evaluated in the clinic, or alternatively, an optional site-specific local laboratory.

NOTE: For subjects randomized to the edoxaban arm, a blood sample will be collected before the first dose of edoxaban for PD analysis only if the subject did not receive any heparin (UFH or LMWH) or VKA 24 hours prior to randomization.

- PD blood sample for subjects randomized to edoxaban taken before dosing that day
- Discretionary anti-FXa level and/or aPTT measurement for subjects on SOC with heparin and INR assessment for the subjects on SOC with VKA
- Record any prior and/or concomitant medications used since the last visit.
- Record any AEs since screening visit, including any bleeding events.
- Urine pregnancy test (for post-menarchal females)
- Physical examination for body weight only
- Dispense study drug and record amount (number of tablets/bottles) dispensed. Prescription based, locally sourced SOC study therapy will need to be supported by a prescription identifying the type of SOC to be provided;
- Explain the study drugs and the proper daily dosing to the parent(s) or guardian(s) and subject (if applicable) using the study drug dosing calendar, and confirm that the subject understands the proper daily dosing of study drug.
- Instruct subject to bring all medications including study drug packaging and bottles to each visit (monthly visits even if there are no scheduled procedures).
- Complete the QOL Questionnaire. Note the QOL can be filled out by EITHER a parent or the study participant. The same person should complete the QOL at Month 3.

Parent(s) or guardian(s) or legally acceptable representative parent(s) or guardian(s) and subject (if applicable) will be provided with information detailing symptoms suggestive of bleeding and TE. Parent(s), guardian(s) or subject will be asked to immediately contact the Investigator if these symptoms occur.

The following information may be provided to the parent(s), guardian(s) or subject (information booklet):

- The local medical contact person and emergency telephone number
- The visit schedule
- How to recognize and report signs and symptoms of possible bleeding and thromboembolic events (see Section 7.1 and Section 9.1).
- How to use the study drugs and instructions to keep empty medication packages

- Blood collections for assessing the INR will be dependent on the discretion of the Investigator.
- Provide subjects with a subject identification safety card and a prohibited medication card

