2.3.4. Pharmacokinetic (PK)/Pharmacodynamic (PD)/Biomarker Endpoint(s)

Plasma concentrations of edoxaban and its metabolite, D21-2393, will be assessed in subjects who receive at least 1 dose of edoxaban treatment and have measurable concentrations of edoxaban and/or D21-2393. Population PK analysis will be conducted to characterize the PK profiles of edoxaban in this target subject population.

The PD biomarkers of coagulation, PT, activated partial thromboplastin time (aPTT), and antiactivated Factor X (FXa), will be assessed as secondary endpoints in edoxaban-treated subjects.

Other biomarkers may be tested related to coagulation and/or edoxaban's mechanism of action.

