5.2.4.1. To Initiate Edoxaban Treatment at Randomization

For subjects without prior anticoagulant therapy, edoxaban may be started the day of randomization (Day 1).

For subjects who received VKA treatment prior to randomization and are randomized to edoxaban, VKA treatment will be discontinued the day before randomization and edoxaban dose will be initiated when an INR \leq 2.5 is reached. It is per Investigator's discretion based on his/her local practice and on the subject's underlying cardiac disease to consider if heparin bridging is necessary during this period. Heparin bridging will be provided by the Investigator.

If heparin bridging is used, edoxaban will be started as below:

- 1. In case of bridging with a LMWH twice a day regimen, edoxaban dosing will start 12 ± 3 hours after the last LMWH dose
- 2. In case of bridging with a LMWH once a day regimen, edoxaban dosing will start 24 ± 3 hours after the last LMWH
- 3. In case of bridging with a UFH regimen, edoxaban dosing will start 4 ± 1 hour after the last UFH dose

5.2.4.2 Transition SOC-Treated Subjects during the Main Treatment Period to Edoxaban in the Extension Period

For subjects who received VKA treatment edoxaban dosing will be initiated when an INR \leq 2.5 is reached. This may occur as early as next day of the Extension Period.

If the subject was originally randomized to UFH or LMWH, edoxaban will be started as below:

1. In case of LMWH twice a day regimen, edoxaban dosing will start 12 ± 3 hours after the last LMWH dose

- 2. In case of LMWH once a day regimen, edoxaban dosing will start 24 ± 3 hours after the last LMWH
- 3. In case of UFH regimen, edoxaban dosing will start 4 ± 1 hour after the last UFH dose

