- ^p At Day 1, Visit 2 (at Randomization), one PD sample will be collected prior to first dose of edoxaban in tubes with citrate sodium as anticoagulant and at Month 1 Visit 3, one sample will be collected between 1 to 3 hours after the edoxaban dose at the same time of PK specimen. For subjects randomized to the edoxaban arm, a PD blood sample will be collected only if the subject did not receive any heparin (UFH or LMWH) or VKA within a 24-hour wash-out period prior to randomization.

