17.2. Recommendations per CHEST 2012 Guidelines¹¹

Table 17.2 shows the initial treatment and prophylactic doses of LMWH that are used in pediatric subjects based on age.

Drug	Age	Initial Treatment Dose	Initial Prophylactic Dose
Age-Dependent Dose	<2 months	1.5 mg/kg/dose q12h	0.75 mg/kg/dose q12h
of Enoxaparin	>2 months	1.0 mg/kg/dose q12h	0.5 mg/kg/dose q 12h
Enoxaparin has 110 anti-	-Factor Xa uni	ts/mg	
Recommended target and	ti-FXa range fo	or LMWH is 0.5 to 1.0 IU/mL.	
Note: The anti-FXa assa inhibition of Factor Xa is	y detects hepain n the assay rea	rin in subject's plasma based on gent.	

 Table 17.2:
 Doses of LMWH (enoxaparin) Used in Pediatric Subjects

Table 17.3 shows the protocol for anticoagulation therapy to maintain an INR between 2 and 3 for pediatric subjects on warfarin therapy.

Table 17.3:Protocol for Anticoagulation Therapy to Maintain an INR Between 2 and 3
for Pediatric Subjects (Warfarin Treatment)

1	Day 1: if the baseline INR is 1.0 to 1.3: Dose 0.2	mg/kg orally
	·	
2	Loading 0.2 mg/kg Days 2-4: if the INR is:	
	INR	Action
	1.1 – 1.3	Repeat initial loading dose
	1.4 - 1.9	50% of initial loading dose
	2.0 - 3.0	50% of initial loading dose
	3.1 – 3.5	25% of initial loading dose
	>3.5	Hold until INR <3.5; then restart at 50% decreased dose
3	Maintenance oral anticoagulation dose guidelines	:
	INR	Action
	1.1 -1.4	Increase by 20% of dose
	1.5 – 1.9	Increase by 10% of dose
	2.0 - 3.0	No change
	3.1-3.5	Decrease by 10% of dose
	>3.5	Hold until INR <3.5; then restart at 20% decreased dose

Abbreviations: INR = international normalized ratio

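### The 24-hour wash-out for the Day 1 PD sample treats VKA like heparin, so Day 1 PT in children switched from VKA can still carry VKA effect

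*Combined protocol and SAP*

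**What the plan says.** PT, aPTT and anti-FXa "will be assessed as secondary endpoints in edoxaban-treated subjects" (Section 2.3.4). Section 8 names anti-FXa activity as the primary PD biomarker. Section 8.2 schedules one sample on Day 1 before the first edoxaban dose and one at Month 1, 1 to 3 hours after a dose, with a further sample at a TE or a major or CRNM bleed.

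The safeguard on the Day 1 sample is in Section 6.3: it is taken "only if the subject did not receive any heparin (UFH or LMWH) or VKA 24 hours prior to randomization". Section 6.4.1 repeats this. Footnote p of Table 17.1 says the same, naming "any heparin (UFH or LMWH) or VKA within a 24-hour wash-out period prior to randomization".

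On switching, Section 5.2.4.1 says that "VKA treatment will be discontinued the day before randomization", with edoxaban to begin once INR is 2.5 or lower. Section 5.1.1 has such subjects treated on Day 1 itself if INR is at or below that value. Section 5.2.1.2 gives the VKA therapeutic range as INR 2 to 3. Children already anticoagulated are eligible (Section 4.1, criterion 1b).

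Section 11.4.2 summarises PD measures descriptively, broken down by age, dose and sampling time. It does not split by prior anticoagulant.

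**The concern.** The evident purpose of the wash-out rule is to keep earlier anticoagulant out of the pre-dose sample. One day off treatment is applied to heparin and VKA alike. Section 1.2 explains that VKAs act indirectly, by blocking synthesis of factors II, VII, IX and X, so hours since the last tablet do not measure the remaining effect. The switching rule itself takes for granted that INR may still be raised at this time. INR is calculated from PT, so a raised INR is a prolonged PT.

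What is at stake is the only scheduled PD sample before edoxaban, which cannot be repeated once dosing starts. If it is summarised across all edoxaban subjects, the Day 1 PT column describes two different states. A reader who sets it beside Month 1 will see too small an edoxaban effect on PT, or one in the wrong direction.

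**Working it through.** The plan gives no figure on this point to reproduce. The check has two parts.

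**1. Can both rules be met with VKA effect still present?**

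- Sampling rule (6.3, 6.4.1, footnote p): no VKA in the 24 hours before randomization; INR is not mentioned.
- Dosing rule (5.1.1, 5.2.4.1): INR of 2.5 or lower.
- Therapeutic range (5.2.1.2): INR 2 to 3.

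A child whose last VKA dose was just over 24 hours before randomization, with an INR between 2.0 and 2.5, satisfies both rules, gives the sample and is dosed. The overlap follows from the text alone.

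As an illustration, assume that (INR − 1) halves every 24 to 48 hours. Then INR at 24 hours = 1 + (start − 1) × 0.5^(24/half-life):

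- start 2.5: 1 + 1.5 × 0.50 = 1.75, up to 1 + 1.5 × 0.71 = 2.06
- start 3.0: 1 + 2.0 × 0.50 = 2.00, up to 1 + 2.0 × 0.71 = 2.41

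All four values pass the 2.5 limit.

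**2. How large could the effect on PT be?**

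INR = (PT ratio)^ISI, so PT ratio = INR^(1/ISI). The documents give no ISI; 0.9 to 1.5 is assumed.

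| INR | ISI 0.9 | ISI 1.0 | ISI 1.5 |
|---|---|---|---|
| 2.0 | 2.16 | 2.00 | 1.59 |
| 2.5 | 2.77 | 2.50 | 1.84 |

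Let f be the share of Day 1 samples from children with recent VKA and b their PT ratio, with 1.0 for the others. The pooled Day 1 mean is 1 + f(b − 1). Neither f nor b is in the documents. If someone computed a change to an assumed Month 1 PT ratio of 1.5 (true change +0.50):

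| f | b | Pooled Day 1 mean | Apparent change |
|---|---|---|---|
| 20% | 1.5 | 1 + 0.2 × 0.5 = 1.10 | +0.40 |
| 40% | 2.0 | 1 + 0.4 × 1.0 = 1.40 | +0.10 |
| 60% | 2.5 | 1 + 0.6 × 1.5 = 1.90 | −0.40 |

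The last row is an extreme: it puts every affected child at the highest INR allowed (ISI 1).

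**Two related details.** Table 17.1 schedules INR at Screening for all subjects and after randomization for SOC subjects, and Section 6.3 leaves INR blood collection to the investigator. So the INR that the dosing rule requires has no scheduled place beside the PD sample. Also, the 24 hours run back from randomization, not from the blood draw. Heparin bridging given while waiting for INR to fall (5.2.4.1) would not breach the sampling rule.

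**The case against.** A reader might infer that the edoxaban PT endpoint as a whole is distorted, even reversed in sign. The documents do not support that. Section 11.4.2 specifies no PD change from baseline; where the plan wants one, for laboratory results and vital signs (11.4.3.4, 11.4.3.5), it says so. The models it describes are population PK on concentrations and exposure-response for safety and efficacy endpoints if data allow, not a model with Day 1 PT as untreated reference. The Month 1 PT is the on-edoxaban measurement, about 30 days after randomization, and the Day 1 rule does not alter it. Anti-FXa is the primary PD biomarker; the note to Table 17.2 describes that assay as working through Factor Xa in the reagent, so residual VKA is no reason to discard it. All of this stands.

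A reader might also take 1.0 to 1.3 in Table 17.3 as the protocol's untreated INR range. The table says "if the baseline INR is 1.0 to 1.3" only as a condition for a warfarin loading dose, and it lists overlapping values on Days 2 to 4 of loading and during maintenance. It is not a reference range.

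The number of children affected may be small. Anyone whose last VKA dose fell within 24 hours gives no sample, and Section 8.2 samples only where blood volume permits. Unequal distortion across age groups is plausible but not shown. Finally, Section 5.5 already records anticoagulants for 3 months, so a split by prior VKA is possible with existing data, and Section 11.7 leaves the handling of spurious data to the SAP. That makes the remedy easy. It does not supply it, since the available text contains no such split or rule.

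**Conclusion.** The concern holds in a limited form. The 24-hour rule does not ensure a Day 1 sample free of VKA effect, and the protocol's own INR limit for starting edoxaban shows that such an effect may be present. The Day 1 PT, and possibly aPTT, in children with recent VKA is affected, and with it the pooled Day 1 summary and any comparison of that summary with Month 1. Month 1 values, anti-FXa and the primary bleeding comparison are not affected.

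The mechanism follows from the text together with the fact that INR is derived from PT. The size does not: the PT ratios rest on an assumed ISI, and the apparent changes of +0.40 to −0.40 rest on assumed shares, baseline ratios and Month 1 ratio, for an analysis the plan does not specify. This is an inexpensive improvement to a descriptive secondary PD analysis in a study not powered for comparisons, not a threat to its main conclusion.

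**What to change.** - **Data collection (6.3, 6.4.1, 8.2, footnote p):** with each Day 1 PD sample, record the pre-dose INR that prior-VKA subjects already need under 5.1.1 and 5.2.4.1, and the time of the last VKA or heparin dose, including any bridging dose after randomization.
- **Summary (11.4.2):** present Day 1 PT and aPTT separately for recent VKA, recent heparin and neither. Define recent in the SAP before database lock.
- **Comparisons and models:** base any baseline-to-Month 1 PT/aPTT comparison, or baseline-adjusted PD model, on subjects without recent VKA or with a pre-dose INR inside the local laboratory's normal range. Do not use Table 17.3 for this threshold.
- **Unchanged:** keep anti-FXa for all subjects, and leave the rule for starting edoxaban as written.

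The cost is a few recorded fields, a flag in the PD dataset and one more split in the tables. The downside is fewer usable baseline PT/aPTT values; the others are still shown, in their own column.

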6.4. Main Treatment Period

The Main Treatment Period is defined as the time from randomization until the end of Month 3 of treatment. All treatment comparative analyses will be made during this time period.

6.4.1. Subjects Randomized to the Edoxaban-Treatment Arm:

For subjects randomized to the edoxaban arm, a blood sample will be collected before the first dose of edoxaban for PD analysis only if the subject did not receive any heparin (UFH or LMWH) or VKA 24 hours prior to randomization.

6.4.2. Subjects Randomized to the SOC-Treatment Arm:

SOC will be provided by the Investigator. Alternatively, local supply depots within each country will provide SOC directly to the clinical sites. Subjects will be treated with heparin (UFH or LMWH) or VKA according to the site's SOC treatment procedure. However, if there are regulatory or clinical site hurdles providing the SOC, the Sponsor will provide SOC as enoxaparin or warfarin (see below).

If Investigators choose to use the SOC supplied by the Sponsor, the subject will be treated as follows:

- Enoxaparin Subjects will be treated with enoxaparin alone or as a bridging therapy in combination with warfarin during the initial study treatment period.
- For subjects in whom clinicians prescribe warfarin, this will be started on Day 1. Heparin bridging prior to reaching therapeutic levels by INR with warfarin may be performed depending on the clinical site's practice. Bridging therapy will be provided by the Investigator for the short duration. The subject will continue warfarin for the remainder of the study treatment period.

The Investigator will use discretion to decide when and how often to repeat INR or anti-FXa levels or aPTT measurements. These measurements will be taken in the clinic, or alternatively, optional clinical site-specific local laboratory (Appendix 17.1).

6.4.3. Monthly Visits (Months 1 and 2; Visits 3 and 4) for both arms:

Starting with Randomization, subjects will return to the clinic every 30 days ± 5 days (depending on the visit, see Schedule of Events in Appendix 17.1) until the Month 3 visit (Visit 5) or study withdrawal.

During study drug interruptions and after study drug discontinuation, subjects will be followed for the protocol-specified study procedures to assess the efficacy and safety endpoints and SAEs until the Month 3 visit (Visit 5). If a subject discontinues study drug prior to The Main Treatment

Period completion, the subject will continue to follow the protocol procedures to Month 3 visit and have a 30-day Follow-Up Visit (Visit 9).

At these monthly on-site visits, discretionary anti-FXa levels assessments and/or aPTT measurements will be performed for the subjects on SOC with heparin and INR assessments will be performed for the subject on SOC with VKA. Additional interim visits may be scheduled, at the Investigator's discretion, for anti-FXa levels and/or aPTT and INR monitoring. All therapeutic monitoring of SOC will be performed locally.

6.4.3.1. Month 1 Visit (Visit 3) Procedures

The following will be performed at this visit:

- Record concomitant medications
- Count unused study drug tablets/bottles/syringe and calculate compliance
- Dispense study drug medication and review dosing instructions
- Perform physical examination see Section 9.9 including:

Vital signs (BP, heart rate, and body temperature after resting in a sitting or supine position [Note: the appropriate cuff size base on arm circumference will be used]).

Height and body weight (may be performed by an Investigator or other healthcare provider designated by the Investigator).

- Urine pregnancy test in females of child bearing potential.
- Take blood samples for the following laboratory tests:

LFTs (ALT, AST, TBL, and ALP)

Serum creatinine and eGFR assessment

PK only (pre-dose)

PK/ PD blood samples (one time point between 1 and 3 hours post-dose for edoxaban-treated subjects)

- Discretionary anti-FXa level and/or aPTT measurement for subjects on SOC with heparin and INR assessment for the subjects on SOC with VKA.
- Safety review for AEs/SAEs
- Review for symptomatic endpoint events (bleeding, symptomatic TE with supporting imaging)

